8.2.4.3 Management of Results

Participants will be contacted if a clinically actionable gene variant is discovered on research testing. Clinically actionable findings for the purpose of this study are defined as disorders appearing in the American College of Medical Genetics and Genomics recommendations for the return of incidental findings that is current at the time of primary analysis. Participants will be contacted at this time with a request to provide a blood sample to be sent to a CLIA certified laboratory. A provider on the study team with training or practice experience in genetics will discuss the results with the participants.

This is the only time during the study that incidental findings will be returned. No interrogations regarding clinically actionable findings will be made after the primary analysis.

8.2.4.4 Genetic counseling

Genetic counseling and discussion of results will be done by a provider on the study team with training or practice experience in genetics.

8.3 SAFETY AND OTHER ASSESSMENTS

The specific timing of procedures/evaluations to be done at each study visit are captured in **Section 1.3, Schedule of Activities**. Direct evaluations (e.g., Device training, Feasibility test) at Screening, Enrollment Baseline Day 1 and 1-Week Evaluations Day 5 visits will be done onsite at the NIH CC. Non-direct evaluations (e.g., surveys and questionnaires) and evaluations on other study days can be done onsite or at home.

- 1. Medical History and Physical Exam.** A medical history and physical exam will be obtained. For CLN3 participants, medical history will ascertain information that is being collected as part of a national CLN3 registry (<https://rarediseases.info.nih.gov/diseases/5897/neuronal-ceroid-lipofuscinosis-3>). Participation in the registry is not a requirement and caretakers or participants will be given the option of having medical information submitted to the registry. The history forms contain common data elements recommended for rare diseases research. Parents and participants may also be asked what elements of the disease are clinically relevant to them, in order to obtain insight into pertinent outcome measures in designing future therapeutic trials. Information from outside records or NIH visits, and from reports by participants and family members will be collected and reviewed.
- 2. Anthropomorphic Measures and Clinical Photography.** Anthropomorphic measures including weight, length/height, and head circumference will be obtained at each visit.
- 3. Feasibility Questionnaire.** Participants/parents/guardians will be asked to complete a questionnaire relating to their experience using the OrCam device (**Appendix B**). The questionnaire can be completed on paper or web-based format at the time points indicated in the **Schedule of Activities**.

4. **Device Training.** A study team member will provide verbal instructions to participant and parents/guardians on the assembly, set-up, and use of the OrCam. The instructions will be based on the User Guide (**Appendix J**). At the end of the training session, understanding of how to use the device will be documented by the trainer.
5. **Device Use Diary.** As described in **Section 6.4 Study Intervention Compliance**.
6. **Adverse Events Review.** A study team member will contact the family at the times indicated in the Schedule of Activities to collect information on adverse events relating to the use of OrCam MyEye 2. During this interaction, study team member will also review the Device Use Diary with the family and provide assistance to trouble shoot any issue relating to the use of the device.
7. **Clinical Staging.** For CLN3 participants not co-enrolled in protocol 18-CH-0002, clinical staging will be performed using the Unified Batten Disease Rating Scale (UBDRS). The UBDRS was developed to provide a tool to quantify physical, behavioral and functional aspects of juvenile neuronal ceroid lipofuscinosis [30]. Data from the ophthalmological, neurological, neurocognitive and speech evaluations will be integrated to obtain a UBDRS score for each participant. This tool has been shown to be a reliable instrument [30] and has been utilized in a retrospective evaluation of flupirtine [31] and prospectively for mycophenolate mofetil (<https://clinicaltrials.gov/ct2/show/NCT01399047?term=CLN3&rank=2>)
8. **Biomaterials Collection.** To complement the CLN3 Natural History (18-CH-0002) protocol's objective to identify biochemical markers, biospecimens will be collected from CLN3 participants who are not co-enrolled in 18-CH-0002. Participants will be consented for broad use and future research on the collected biomaterials. The method of analysis for biomarker discovery is not specified. Applicable technologies include but are not limited to proteomics, lipidomics, expression analysis, gene/exome/genome/transcriptome sequencing, metabolomics, and multi-analytes profiling. Subcomponents of a sample, such as exosomes, may be isolated and studied. Comparisons will be made to age similar control samples, made up in part by those collected from the non-CLN3 participants in this study. Since the function of CLN3 protein is incompletely understood, the objectives for biomarker discoveries are broad and may include those such as identifications of compounds in the plasma or urine whose level correlate with disease progression or with future therapeutic interventions.

Collected cells may be used to produce cellular derivatives such as lymphoblasts, immortalized cell lines, or induced pluripotent stem cells. Coded samples will be maintained in the NICHD Biorepository and will be made available to collaborating laboratories with appropriate IRB and MTA clearance.

Biomaterials collected as part of this study will include the following:

- blood (such as serum, EDTA plasma and heparin plasma)
- urine
- DNA for CLN3 genotyping, modifier gene analysis or exome/genome sequencing
- dried blood spots on newborn screening cards
- peripheral mononuclear cells
- cheek swabs/scrapings
- saliva

-skin biopsy (3mm or smaller)

Although efforts will be made to obtain as complete a collection as possible, since these samples are collected for discovery research and not for safety monitoring not obtaining a specific sample will not be considered a protocol deviation. Except for blood-related samples, all other biomaterials will only be collected if not already done so under protocol 18-CH-0002.

Identified biospecimens obtained at outside institutions corresponding to study participants already enrolled in the study may be acquired under this protocol. These samples could be obtained secondary to clinical procedures (such as surgical specimens, clinical blood testing, or autopsy) or obtained as part of another ongoing clinical trial. Study participants will be consented to allow for the identifiable samples to be sent to NIH. These samples will be treated the same as a research specimen that was collected at the NIH Clinical Center. Unless needed for an ongoing experiment or requiring specific storage conditions other than -80 degrees Celsius, samples will be coded and stored in the NICHD Biorepository.

9. **Phlebotomy.** We anticipate collecting a maximum of 80 mL (5-6 tablespoons) of blood per participant. If more than one blood collections are needed (e.g., because of severe hemolysis) we will not exceed the 5 ml/kg/day, or 9.5 mL/kg over any 8-week period limits. Nursing staff will monitor blood-drawing volumes.
10. **Cheek swabbing/scraping and saliva collection.** We will use commercially available kits and follow the manufacturer's instructions.
11. **Skin biopsy.** A local anesthetic may be applied prior to the procedure. A 2-3 mm punch biopsy of the skin will be removed using sterile technique, and the wound will be dressed.
12. **Urine collection.** We may use a urine cup or toilet hat to collect urine. Participants will not be catheterized for this study.
13. **Outside records.** Under this protocol we may collect non-NIH Clinical Center outside records such as medical and research corresponding to participants or family members of participants. Typically, these records will be provided directly by the participant/guardian. A release of records request signed by the participant/guardian will be used if obtaining records from other health care providers. Information from these records may be incorporated into study databases. These records and personal identifying information will be maintained confidentially.
14. **Future Research.** Biomaterials, records, and data collected as part of this protocol may be used for future research not specifically specified in this protocol by both NIH and non-NIH investigators. Samples sent to outside laboratories will be coded, unless a standard clinical test is being performed. Materials Transfer Agreements will be obtained as applicable for samples sent to collaborators.
15. **Return of results and community engagement.** Participants will have access to all clinical testing and evaluation results through the NIH Clinical Center Portal. Protocol status is reviewed with participating families. Research results will be presented to the disease community via presentations or updates to the family support groups. Copies of publications related to this research will also be made available to the family support groups. The trial will be registered on clinicaltrials.gov and results will be posted per standard requirements.

The concept for this study arose from parental responses from the CLN3 natural history study. When asked to rank in order (1=most desirable) the symptoms they would like to see being addressed by future interventions, 37% of mothers (n=19) and 47% of fathers (n=15) chose vision as number one. A family of a child with CLN3 brought the OrCam MyEye 2 device to the study team's attention, and their observations on its use has been incorporated into the study design.

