1 PROTOCOL SUMMARY

1.1 SYNOPSIS

Title:	Pilot Study of an Optic-to-Audio Device in a Pediatric Cohort with CLN3-related conditions or Low Vision
Study Description:	This is a pilot study of an augmentative visual device, OrCam MyEye 2 (OrCam), in pediatric individuals with CLN3-related conditions or low vision. We hypothesize that, given the relatively simple design and operating procedure of the device, the use of the OrCam by study participants will be safe and feasible. We also hypothesize that the device will enhance their ability to obtain visually based information.
Objectives:	
Primary Assess the safety and feasibility of OrCam use by children with CLN3 or low vision.
 
Secondary Assess the effectiveness of OrCam use by children with CLN3 or low vision.
 
Exploratory Assess the feasibility and effectiveness of OrCam use in CLN3 versus non-CLN3 groups. Optimize methods for assessing efficacy of visual accommodation/assistive devices for the CLN3/NCL population

Endpoints:	
Primary 1) Adverse events during the use of OrCam. 2) Feasibility test. 3) Feasibility questionnaire. 4) Device use diary. The assessment periods will be 1 week at study site and 1 month at home.
 
Secondary 1) Function test of using OrCam. 2) Ability questionnaire.
 
Exploratory 1) Function test. 2) Feasibility, Ability, Applicability questionnaires.

Study Population:	30 individuals age 6-18 years with low vision (20 with CLN3-related conditions, 10 without CLN3) of any gender, demographic, geographic location who meet study eligibility criteria.
Phase:	Not applicable
Description of Sites/Facilities	The NIH Clinical Center will be the only site enrolling participants.
Enrolling Participants:	
Description of Study Intervention:	The study uses the OrCam MyEye 2, a 22.5-g portable, eyeglass-mounted device that converts camera-captured inputs to auditory outputs. Its advertised functions include text reading, facial recognition, and product identification. The study participants and

Abbreviated Title: Pediatric Optic-to-Audio Device Study

[figure not shown]
Version Date: October 25, 2022

parents/guardians will be trained on how to use the device. Evaluations for primary and secondary endpoints will be done following 1 week and 1 month of device use.

Study Duration: 24-36 months.

Participant Duration: 1-2 months

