8.4 ADVERSE EVENTS AND SERIOUS ADVERSE EVENTS

8.4.1 Definition of Adverse Event

Adverse event means any untoward medical occurrence associated with the use of an intervention in humans, whether or not considered intervention-related (21 CFR 312.32 (a)).

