8.4.3.2 Relationship to Study Intervention

All adverse events (AEs) must have their relationship to study intervention assessed by the investigator who examines and evaluates the participant based on temporal relationship and his/her clinical judgment. The degree of certainty about causality will be graded using the categories below. In a clinical trial, the study product must always be suspect.

- **Related** – The AE is known to occur with the study intervention, there is a reasonable possibility that the study intervention caused the AE, or there is a temporal relationship between the study intervention and event. Reasonable possibility means that there is evidence to suggest a causal relationship between the study intervention and the AE.
- **Not Related** – There is not a reasonable possibility that the administration of the study intervention caused the event, there is no temporal relationship between the study intervention and event onset, or an alternate etiology has been established.

OR

- **Definitely Related** – There is clear evidence to suggest a causal relationship, and other possible contributing factors can be ruled out. The clinical event, including an abnormal laboratory test result, occurs in a plausible time relationship to study intervention administration and cannot be explained by concurrent disease or other drugs or chemicals. The response to withdrawal of the study intervention (dechallenge) should be clinically plausible. The event must be pharmacologically or phenomenologically definitive, with use of a satisfactory rechallenge procedure if necessary.
- **Probably Related** – There is evidence to suggest a causal relationship, and the influence of other factors is unlikely. The clinical event, including an abnormal laboratory test result, occurs within a reasonable time after administration of the study intervention, is unlikely to be attributed to concurrent disease or other drugs or chemicals, and follows a clinically reasonable response on withdrawal (dechallenge). Rechallenge information is not required to fulfill this definition.

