8.4.4 Time Period and Frequency for Event Assessment and Follow-Up

The occurrence of an adverse event (AE) or serious adverse event (SAE) may come to the attention of study personnel during study visits and interviews of a study participant presenting for medical care, or upon review by a study monitor.

All AEs including local and systemic reactions not meeting the criteria for SAEs will be captured on the appropriate case report form (CRF). Information to be collected includes event description, time of onset, clinician's assessment of severity, relationship to study product (assessed only by those with the training and authority to make a diagnosis), and time of resolution/stabilization of the event. All AEs occurring while on study must be documented appropriately regardless of relationship. All AEs will be followed to adequate resolution.

Any medical condition that is present at the time that the participant is screened will be considered as baseline and not reported as an AE. As CLN3 is a neurodegenerative, multisystemic disease, progression or new onset of symptoms may be part of the disease process and unrelated to the intervention. Problems listed in **Table 2** will not be reported to the IRB as adverse events unless increase in frequency is noted.

Changes in the severity of an AE will be documented to allow an assessment of the duration of the event at each level of severity to be performed. AEs characterized as intermittent require documentation of onset and duration of each episode.

A designated study team member will record all reportable events with start dates occurring any time after informed consent is obtained until 7 (for non-serious AEs) or 30 days (for SAEs) after the last day of study participation. At each study visit, the investigator will inquire about the occurrence of AE/SAEs since the last visit. Events will be followed for outcome information until resolution or stabilization.

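### Section 8.3 item 6 words the scheduled adverse event contacts more narrowly than 8.4.4 and the primary endpoint, which risks under-ascertainment at the Day 12, 19 and 26 home contacts

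*Combined protocol and SAP*

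**What the plan says.** Section 8.3 item 6 describes the adverse events review in the Schedule of Activities (Section 1.3). A team member contacts the family at the scheduled times "to collect information on adverse events relating to the use of OrCam MyEye 2", goes through the device use diary and helps with device problems. The schedule places this review on Days 5, 12, 19, 26 and 33. Days 12, 19 and 26 are at home; Days 5 and 33 may be at the NIH or at home.

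Four other places are broader:

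- Section 8.4.1 defines an adverse event "whether or not considered intervention-related".
- Section 8.4.4 states: "All AEs occurring while on study must be documented appropriately regardless of relationship".
- Section 8.4.3.2 says that all adverse events "must have their relationship to study intervention assessed by the investigator who examines and evaluates the participant". On its two-category scale, an event counts as related if any one of several conditions holds, the last being "or there is a temporal relationship between the study intervention and event".
- The synopsis gives the first primary endpoint as "Adverse events during the use of OrCam", which is a limit on time and not on cause.

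Section 8.4.4 also provides a second route: "At each study visit, the investigator will inquire about the occurrence of AE/SAEs since the last visit". It carries no relatedness limit.

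**The concern.** A contact that asks about events relating to the device invites the family to judge causality before the investigator sees the event. The family's filter may be stricter than the protocol's own, since 8.4.3.2 accepts timing alone as grounds for calling an event related.

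Three features of this trial make that matter:

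- **Overlap of device effects and disease symptoms.** Section 2.3.1 expects that the added sound may irritate and that getting used to the device may frustrate. The table of CLN3-associated events in 8.4.5 lists irritability, aggression, anxiety, sleep disruption and falls. A parent could reasonably put such an event down to the disease.
- **Possible difference between cohorts.** Twenty of the 30 planned participants have a multisystem disease to which events can be attributed; the other 10 do not have CLN3. Section 9.4.7 applies the 9.4.2 analyses, which include adverse events, to the sub-groups. A difference in reporting could look like a difference in safety.
- **The protocol's own trigger.** Section 8.4.4 exempts the listed CLN3 problems from IRB reporting unless they become more frequent. A rise can be noticed only if these events are asked about whatever their supposed cause.

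There is no data safety monitoring committee (10.5), and the safety analysis is descriptive (9.4.2). A shortfall in collection would not show up in the summary.

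**Working it through.** The plan states no adverse event rate, safety threshold or safety power, so it has no figure to reproduce. The check is a comparison of the text, followed by an illustration.

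**1. Scope of each rule**

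| Place | Which events | Who judges cause |
|---|---|---|
| Synopsis, primary endpoint | those during device use | not stated |
| 8.4.1 | all, related or not | not part of the definition |
| 8.4.3.2 | all | investigator |
| 8.4.4, documentation rule | all on study | clinician, after recording |
| 8.4.4, visit inquiry | all since the last visit | not limited by cause |
| 8.3 item 6, scheduled contacts | those relating to the device | implicitly whoever answers |

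Item 6 is the only one that restricts by cause.

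**2. Which scheduled days depend on item 6**

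- Days 5 and 33 are evaluation visits, so the 8.4.4 visit inquiry applies as well. Section 5.7.2 calls the 1-month assessment a visit even when it is remote.
- Days 12, 19 and 26 are home reviews. Section 6.4 calls the weekly reviews contacts, so it is unclear whether the visit inquiry reaches them. They are the only scheduled adverse event contacts between Days 5 and 33.

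**3. Recall period (nominal days; the schedule allows plus or minus 2)**

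- With weekly contacts: 12 − 5 = 19 − 12 = 26 − 19 = 33 − 26 = 7 days.
- If an event is left to the Day 33 visit inquiry: up to 33 − 5 = 28 days.

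Section 8.4.4 also asks for changes in severity and for the onset and duration of each intermittent episode. Those details are harder to recover over 28 days than over 7.

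**4. Illustration only**

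Let *c* be the fraction of participants with a given type of event whose event is recorded. The documents give no value for *c* and do not show that it is below 1. The values below are assumptions, with N = 30.

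- After zero recorded events, the one-sided 95% upper bound on the recorded rate is 1 − 0.05^(1/30) = 9.5%. The bound on the true rate is 9.5%/*c*.
- For an assumed true rate of 10% per participant, the chance of recording at least one event is 1 − (1 − 0.10*c*)^30.

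| *c* (assumed) | Upper bound on true rate after zero recorded | Chance of at least one recorded, true rate 10% |
|---|---|---|
| 1.00 | 9.5% | 0.958 |
| 0.90 | 10.6% | 0.941 |
| 0.75 | 12.7% | 0.904 |
| 0.50 | 19.0% | 0.785 |

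The table shows how sensitive a small descriptive safety summary is to incomplete capture. It does not estimate the loss in this trial.

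**The case against.** The strongest reply is that 8.4.4 already closes the gap. The investigator asks about all adverse events at every study visit, and the question at Day 33 reaches back over the home period. The same section binds the staff who make the calls, so they must document any event they hear of. There are other routes too: interviews and monitor review (8.4.4), daily diary cross-checks in the first week (6.4), a safety evaluation sought about a week after last use before removal from the study (7.2), and typically weekly staff meetings (10.5). Item 6 states the purpose of the contact and does not say that other events are to be ignored. No contact script is in the documents, so the actual question cannot be seen. Conditions present at screening are baseline under 8.4.4, which narrows what is at stake. The home phase is voluntary (6.1.1, 6.3), so participants who stop after the first week have no home contacts to be affected.

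Much of this stands. A reader might infer that unrelated events are never elicited, that all five scheduled reviews are compromised, or that the safety endpoint is under-counted by some definite share. The documents support none of these: Days 5 and 33 carry an unrestricted inquiry, item 6 contains no exclusive wording, and no figure for lost events is given or derivable.

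The reply does not remove the inconsistency. The schedule lists one adverse event procedure, and item 6 is its operating instruction. The visit inquiry clearly covers only the two ends of the home period. A duty to document does not help if the question asked does not bring the event out.

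**Conclusion.** The inconsistency is real and stands in the current text. The instruction for the scheduled contacts is narrower than the adverse event definition, the documentation rule, the assignment of causality and the primary endpoint. Its practical effect is a risk of under-ascertainment and longer recall, about 28 days instead of 7, mainly at Days 12, 19 and 26. That risk may differ between the CLN3 and non-CLN3 cohorts, and it weakens the trigger for reporting a rise in CLN3-type events.

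This rests on two assumptions: that staff take item 6 at its word during the home contacts, and that some families attribute new or more frequent symptoms to CLN3. Neither can be confirmed from the documents, and the size of any loss cannot be calculated. No sample size, power figure or decision rule changes. The point is still worth correcting, because adverse events are a primary endpoint and events missed during the home month may not be recoverable later.

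**What to change.** Reword the first sentence of 8.3 item 6 so that the team member contacts the family to *collect information on all adverse events since the last contact, regardless of perceived relationship to the device*. Add that relationship is assigned afterwards by the investigator under 8.4.3.2. The diary review and troubleshooting can stay as they are.

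The change adds no visits or contacts. Calls may run slightly longer and more unrelated events will be recorded, but 8.4.4 already requires those records.
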